6.3 Interim Analyses

An IA of data collected in this study will be performed after the database lock and study unblinding of parent studies ARQ-151-311 and ARQ-151-312. Only data from subjects that rolled over from one of these two parent studies into study ARQ-151-313 will be included in this IA. That is, in order to preserve the blind of parent study ARQ-151-315, which will still be ongoing at the time of ARQ-151-311 and ARQ-151-312 database lock and study unblinding, no data from subjects enrolled in parent study ARQ-151-315 that have rolled over into study ARQ-151-313 will be included in this IA.

Another IA may be conducted at the time of rollovers from these two parent studies complete all scheduled visits in ARQ-151-313. If conducted, similarly to the first IA, only data from subjects

 Innovaderm Research	STATISTICAL ANALYSIS PLAN, Final Version 1.0
Protocol Number: ARQ-151-313	Sponsor: Arcutis Biotherapeutics, Inc.

that rolled over from one of these two parent studies into study ARQ-151-313 will be included in the IA in order to preserve the blind of parent study ARQ-151-315.

All analyses planned in this SAP will be performed at the time of the IA.

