4. INVESTIGATIONAL PLAN

4.1. Overall Study Design and Plan

This is a Phase 3, open-label, single-arm, long-term safety study in which ARQ-151 cream 0.15% or ARQ-151 cream 0.05% is applied QD x 24 (Cohort-Week 24) or 52 weeks to subjects with mild to moderate atopic dermatitis (except for time on BIW maintenance therapy).

- Eligible subjects will enroll into the long-term safety study on the same day as the Week 4 visit of the preceding study (ARQ-151-311 or ARQ-151-312 or ARQ-151-315).
- Subjects/caregivers will apply ARQ-151 cream 0.15% for subjects \geq 6 years old or ARQ-151 cream 0.05% for subjects 2-5 years old.
- If a 5 year-old subject turns 6 years-old during this study, the subject will be switched from ARQ-151 cream 0.05% to ARQ-151 cream 0.15% at his/her first scheduled post-birthday visit. Dose reduction back to 0.05% is not permitted.
- The study drug will be applied QD for 24 (Cohort-Week 24) or 52 weeks to all AD affected areas and any newly appearing AD lesions that arise during the study, except on the scalp (unless entering BIW maintenance therapy, as described below).
- **For the first 4 weeks of study ARQ-151-313, all subjects will apply study medication QD in the areas identified and treated as per the body diagram in the preceding study (ARQ-151-311/312/315).** Beginning at the Week 4 visit, any subject who achieves vIGA-AD of '0-clear' as confirmed by the Investigator at a scheduled or unscheduled clinic visit, will switch to twice weekly (BIW) maintenance treatment. For maintenance therapy, study medication will be applied on two nonconsecutive days per week (e.g. Monday and Thursday) to areas commonly and/or most recently affected by AD, and any areas where AD is developing. Subjects receiving maintenance treatment who experience AD worsening (signs and symptoms) for 1 week despite dosing twice weekly will phone the clinical study site, resume daily dosing, and complete the subject diary accordingly. The phone call (but not a clinic visit) is required to resume daily dosing. At clinic visits, subjects receiving maintenance treatment may continue twice weekly maintenance dosing if vIGA-AD is either '0-clear' or '1-almost clear'. Subjects will resume daily dosing if vIGA-AD \geq 2, and can resume daily dosing if signs/symptoms of AD are not adequately controlled with maintenance therapy despite vIGA-AD of '1-almost clear'.

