1 INTRODUCTION

This Statistical Analysis Plan (SAP) describes the planned analysis and reporting for Arcutis Biotherapeutics, Inc. clinical protocol ARQ-151-313. The analyses described in the SAP are based upon the protocol Amendment 1 dated 17 September 2021. In case of changes (note that any such changes are described in section 3.6 below) between the protocol and the SAP, the SAP will be used to guide the statistical analysis. Deviations from the SAP are not expected. If any, they will be described and justified in the final Clinical Study Report (CSR), as appropriate.

This version of SAP has been developed and finalized prior to ARQ-151-313 database lock for the first Interim Analysis (IA).

Each IA will be performed only after the following steps have been completed: approval of this SAP, clinical trial data up to a pre-specified data cut-off date are entered into the database for subjects from parent studies ARQ-151-311 and ARQ-151-312 and any discrepancies in the data are resolved, finalization of the classification as important or non-important of each protocol deviation that occurred before or on the pre-specified data cut-off date for subjects from parent studies ARQ-151-311 and ARQ-151-312, and the database is locked. That is, subjects from parent study ARQ-151-315 will not be included in the IAs.

Similarly, the final analysis will be performed only after the following steps have been completed: approval of this SAP, clinical trial data are entered into the database for all subjects and any discrepancies in the data are resolved, finalization of the classification as important or non-important of each protocol deviation, and the database is locked.

ARQ-151 Cream 0.15% and ARQ-151 Cream 0.05% will be described as “roflumilast cream 0.15%” and “roflumilast cream 0.05%” throughout this document and the tables, listings, and figures (TLFs).

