4 POPULATIONS FOR ANALYSIS

4.1 Full Analysis Population

The full analysis population is defined as all subjects who are enrolled in this study.

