- Once the monotone pattern is achieved, the next step is to implement the imputation algorithm. For this, the PMM regression method will be used. This method is particularly helpful if the normality assumption is violated. For subjects with complete data up to a particular visit, a PMM regression model will be fit that includes the outcome at that visit as the dependent variable and as independent variables, the parent study randomized vIGA-AD stratification variable and parent study randomized treatment group, both as categorical variables, as well as the vIGA-AD score outcomes at previous analysis visits, all as continuous variables, using a seed of 482371. This process will be repeated 25 times, resulting in a total of 25 to 250 complete analysis datasets, depending on the number of

 Innovaderm Research	STATISTICAL ANALYSIS PLAN, Final Version 1.0
Protocol Number: ARQ-151-313	Sponsor: Arcutis Biotherapeutics, Inc.

imputed monotone datasets that are required. The seed may be changed after unblinding in case of any issues with the imputation process, and it will be documented in the CSR if any change is required.

3. For each multiply imputed dataset, Primary or OLE Baseline values, as applicable, will be derived as defined Section 5.2 and analysis visits from parent studies (OLE Week -4 to OLE Day 1) not selected as Primary or OLE Baseline, as applicable, will be dropped from each multiple imputed dataset.

For Cohort-Week 24 subjects, imputed OLE Week 36 and Week 52 analysis visit values will be set to missing given that these subjects will complete study at Week 24 or discontinue early from study before Week 24, whichever occurs first.

Finally, for each completed dataset, the vIGA-AD secondary efficacy endpoints will be derived by visit, as described in Section 12.2. Common proportion of success/achievement (and associated standard error [SE]) will then be calculated overall and by treatment group for each OLE analysis visit and combined using PROC MIANALYZE based on Rubin's rule to obtain a combined common proportion of success/achievement for each OLE analysis visit overall and treatment group. The combined common two-sided 95% CI will be calculated as per Lott and Reiter (2020)¹ multiple imputation Wilson interval method

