6.2.2 Non-Responder Imputation

For the vIGA-AD secondary efficacy endpoints (refer to Sections 12.2), missing endpoint values will also be imputed as a non-responder i.e., not achieving the endpoint criteria.

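### At the first interim analysis, the vIGA-AD non-responder and multiple-imputation rules do not exempt visits that are not yet due at the data cut-off

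*SAP*

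**What the plan says.** **Timing.** SAP 6.3: "An IA of data collected in this study will be performed after the database lock and study unblinding of parent studies ARQ-151-311 and ARQ-151-312". SAP 1 adds that, before each IA, "clinical trial data up to a pre-specified data cut-off date are entered into the database"; the date is not given. SAP 6.3 then provides for a second, optional look: "Another IA may be conducted at the time of rollovers from these two parent studies complete all scheduled visits in ARQ-151-313". So the first IA is not tied to completion of follow-up. Protocol 4.1 fixes when follow-up starts: "Eligible subjects will enroll into the long-term safety study on the same day as the Week 4 visit of the preceding study".

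**Scope.** SAP 6.3: "All analyses planned in this SAP will be performed at the time of the IA".

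**Denominator.** SAP 12 bases efficacy on the full analysis set, and SAP 4.1 says: "The full analysis population is defined as all subjects who are enrolled in this study". SAP Appendix 1 makes the size of the population the default denominator for percentages.

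**Handling of missing vIGA-AD.** Under SAP 6.2.2, "missing endpoint values will also be imputed as a non-responder i.e., not achieving the endpoint criteria". SAP 6.2.1 imputes missing vIGA-AD scores for the full analysis set by predictive mean matching (PMM); SAP 12.2.1 makes this the main analysis. The one exemption is in step 3 of 6.2.1: for Cohort-Week 24, "imputed OLE Week 36 and Week 52 analysis visit values will be set to missing". SAP 6.2.2 has no exemption. SAP 12.2.2 also plans an observed-case analysis.

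**The concern.** At a data cut-off, a vIGA-AD value can be absent because the visit was missed, because the subject left, or because the visit has not come due. The third reason says nothing about response; it reflects only the enrolment date. The SAP does not separate it from the other two.

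At stake is how the first IA reads at late visits. An NRI rate would fall with the share of recent enrollees, which has nothing to do with the cream. The main MI table would show Week 24, 36 or 52 proportions for everyone enrolled when some had not reached that visit. Protocol 6 allows early analysis for regulatory reporting, and SAP 1 says this SAP was finalised ahead of the first IA lock with no deviations expected, so the literal wording matters.

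**Working it through.** **1. The SAP's own visit count.** SAP 6.2.1 gives a completer 7 vIGA-AD values (Cohort-Week 24) or 9 (Cohort-Week 52). There are four parent-study values (OLE Week −4, −3, −2 and Day 1). Adding Weeks 4, 12 and 24 gives 4 + 3 = 7; adding Weeks 36 and 52 as well gives 4 + 5 = 9. The figures reproduce. They are full-schedule counts, and 6.2.1 uses them as the expected visits for all subjects in a cohort. Visits due by a cut-off are not mentioned.

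**2. Effect on NRI.** Let p be the response rate if every subject had reached the visit, and f the share not yet due. With no dropout, and f unrelated to response, the reported rate is p × (1 − f). Both inputs are assumptions.

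| p | f = 10% | f = 25% | f = 50% | f = 75% |
|---|---|---|---|---|
| 40% | 36% | 30% | 20% | 10% |
| 50% | 45% | 37.5% | 25% | 12.5% |
| 60% | 54% | 45% | 30% | 15% |

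**3. What f might be.** Accrual is not in the documents. Suppose uniform enrolment over A weeks and a cut-off L weeks after the last OLE Day 1. At Week w, f = (w − L)/A, held between 0 and 1. With L = 8 and p = 50%, each cell shows f, then the NRI rate:

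| A | Week 24 | Week 36 | Week 52 |
|---|---|---|---|
| 26 | 62%, 19% | 100%, 0% | 100%, 0% |
| 52 | 31%, 35% | 54%, 23% | 85%, 8% |
| 78 | 21%, 40% | 36%, 32% | 56%, 22% |

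For example, A = 52 at Week 52: f = (52 − 8)/52 = 0.85, and 0.50 × 8/52 = 0.08. Moving L to 0 or 16 weeks with A = 52 changes f at Week 52 to 100% or 69%. The Week 36 and 52 columns concern Cohort-Week 52 only.

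**4. Effect on MI.** A small PMM simulation (1,000 subjects, one visit imputed from five earlier scores, 25 imputations, 40 repeats, not-yet-due status unrelated to outcome) gave:

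| f | Full-data rate | MI rate | MI SE | Full-data SE |
|---|---|---|---|---|
| 25% | 50.1% | 50.1% | 0.017 | 0.016 |
| 50% | 50.1% | 50.0% | 0.019 | 0.016 |
| 75% | 49.7% | 49.5% | 0.020 | 0.016 |

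MI is about unbiased under that assumption, though a share f of the outcomes behind each rate is model-generated. Where f reaches 100%, PMM has no donors and the visit cannot be imputed.

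One reason for care: Amendment 1 added about 275 + 275 = 550 subjects aged 6 to 17 as Cohort-Week 24, which may tie enrolment date to age. The imputation model has the vIGA-AD stratum, parent treatment and earlier scores, but no age or cohort term. The documents do not show that response differs by age.

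**5. Outputs reached.** Only the two vIGA-AD secondary endpoints (SAP 12.2.1) and their subgroup repeats (SAP 12.2.3) are imputed. WI-NRS and EASI changes are observed-case (SAP 12.2.1), and the other efficacy endpoints are not imputed (SAP 12.3.1).

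**The case against.** The best defence is that this is a silence. The SAP never states that a visit not yet due is missing, and a careful programmer might leave such visits out. Observed-case results would sit beside any depressed NRI rate, NRI is only a sensitivity analysis, no hypothesis tests are planned (SAP 5.7), and missingness by enrolment date is a favourable case for MI. All of this limits the harm. It does not remove the fault: the rules as stated cover all missing values in all enrolled subjects, the one exemption is elsewhere, and different programmers could repair the gap differently.

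A reader might infer more than the documents support:

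- **That both IAs are affected.** The optional second one is timed for when the 311/312 roll-overs have finished their scheduled visits.
- **That the MI results are biased.** That would need later enrollees to differ from earlier ones in ways the model omits, which is possible but not shown.
- **That exposure, durations and disposition lack a workable rule, and should run to the cut-off.** SAP 5.5 already closes or censors open intervals at last contact, and SAP 11 computes exposure from treatment dates in the cut data. Running exposure to the cut-off would add person-time after the last contact, when adverse events have not been ascertained, and so lower the exposure-adjusted rates. Table layouts are in a separate document (SAP 5), so a missing row for ongoing subjects is not established.

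**Conclusion.** The plan is wrong as written, for the first IA only. If f is the share not yet due at a visit, the vIGA-AD NRI rate is reduced by the factor 1 − f: from 50% to 37.5%, 25% or 12.5% for f of 25%, 50% or 75%. The main MI analysis keeps about the right rate if later enrollees resemble earlier ones, but labels partly unobserved visits as results for the whole population.

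The sizes rest on assumed response and accrual. If later 311/312 enrolment was mostly Cohort-Week 24, f at Weeks 36 and 52 would be smaller than in the accrual table. A late enough cut-off would shrink it further.

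Not-yet-due visits do not affect the other efficacy endpoints, the observed-case vIGA-AD analysis, adverse event counts, the optional second IA or the final analysis. One related gap is not confined to the IA: SAP 6.2.2 does not repeat the Cohort-Week 24 exemption. Read literally, that cohort would fail NRI at Weeks 36 and 52, visits it never has. SAP 12.2.2 can be read as inheriting the exemption from the main analysis, but does not say so.

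**What to change.** State in SAP 6.2.1, 6.2.2 and 6.3 that, at an IA:

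- The MI and NRI summaries for a visit include only subjects enrolled early enough for that visit to be due by the data cut-off. Define this by enrolment date, whether or not the subject later discontinued; keeping every discontinuer while dropping ongoing subjects would over-represent dropouts. State the day count that makes a visit due.
- Values imputed for later visits are set to missing, as 6.2.1 already does for Cohort-Week 24.
- The number of subjects not yet due is reported for each visit.
- Observed-case tables keep every observed value, including those of subjects seen before the visit counts as due.

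Repeat the Cohort-Week 24 exemption at Weeks 36 and 52 in SAP 6.2.2. Leave the last-contact rule in SAP 5.5 as it is, and do not extend exposure or duration intervals to the cut-off date.

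The cost is a few sentences of SAP text and one programming flag, with a smaller n at late visits in the first IA tables.

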6.4 Multicenter Studies

Data from all sites will be pooled in the summaries.

6.5 Multiple Comparisons/Multiplicity

No adjustments for multiple comparisons will be made for this study.

6.6 Examination of Subgroups

Subgroup analyses will be performed for the vIGA-AD secondary efficacy endpoints (refer to Section 12.2.3) as well as for the WI-NRS, EASI-50, and EASI-75 endpoints in the other efficacy endpoints (refer to Section 12.3.3) for the following subgroups relative to Primary Baseline only (refer to Section 5.2):

- Age group at informed consent in parent study (2 – 5 years, 6 – 11 years, 12 - 17 years, and \geq 18 years), including the WI-NRS endpoints. That is, although the main analysis for the WI-NRS endpoint in the other efficacy endpoints will be performed on subjects \geq 12 years old, a subgroup analysis will be performed for each of the previously defined age groups, including the 2 – 5 years and 6 – 11 years subgroups.
- Sex (Male and Female)
- Race (White, Black or African American, and Asian vs. Other)
- Ethnicity (Hispanic or Latino and Non-Hispanic or Latino)
- Actual Baseline vIGA-AD score (2- mild and 3- moderate) in parent study
- Prior inadequate response, intolerance, or contraindication to Topical Corticosteroids (yes and no)
- Facial Involvement (yes and no)

Subgroup analyses for rollovers from ARQ-151-311/312 will be performed for the duration, cumulative time, and percent of time other efficacy endpoints (refer to Section 12.3.3) for the following subgroups:

 Innovaderm Research	STATISTICAL ANALYSIS PLAN, Final Version 1.0
Protocol Number: ARQ-151-313	Sponsor: Arcutis Biotherapeutics, Inc.

- Cohort (Cohort-Week 24 and Cohort-Week 52)

Furthermore, to investigate long-term maintenance of the treatment effect, additional subgroup analyses will be conducted on subgroups below that are defined based on post-treatment characteristics. More specifically, subgroup analyses for rollovers from ARQ-151-311/312 will be performed for the BIW dosing and disease control other efficacy endpoints (refer to Section 12.3.3) for the following subgroups (by Cohort and overall):

- Subjects whose first interval started at OLE Week 4
- Subjects with vIGA-AD success at OLE baseline
- Subjects with vIGA-AD score of Clear (0) at OLE baseline

The subgroups criteria a and b as well as a and c will be combined for further subgroup analyses for the BIW dosing and disease control endpoints.

Additionally, the overall summary of treatment-emergent adverse events (TEAE) and summary of TEAEs by system organ class (SOC) and preferred term (PT) (refer to Section 13.1) will be presented by the age groups specified above.

Finally, in order to better understand the efficacy and safety profile of ARQ-151-315 rollover subjects who start this study 5 years old and who turn 6 years old during this study and so, will be switched from roflumilast cream 0.05% to roflumilast cream 0.15% at his/her first scheduled post-birthday visit, analyses will also be performed for this subgroup of subjects. The list of efficacy and/or safety endpoints for which analysis will be performed for this subgroup of subjects will be determined, finalized and approved before the final database lock of parent study ARQ-151-315.

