1.3. Schedule of Visits and Assessments

Study Procedure	Day 1	Wk 4	Wk 12	Wk18	Wk 24 ^t	Wk 30	Wk 36	Wk 44	Wk 52/ET
Visit #	1(Week 4) of ARQ-151-311 or ARQ-151-312 or ARQ-151-315	2	3	Phone Visit	4	Phone Visit	5	Phone Visit	6
Visit Window		+/- 3 days	+/- 7 days	+/- 7 days	+/- 7 days	+/- 7 days	+/- 7 days	+/- 7 days	+/- 7 days
Informed consent/assent	X								
Physical examination ^a	X ^s	X			X				X
I/E criteria	X								
Hematology, Serum Chemistries, and Urine Analysis ^b	X ^s				X				X
Vital signs, height, weight ^c	X ^s	X	X		X		X		X
vIGA-AD, EASI, BSA, SCORAD ^d	X ^s	X	X		X		X		X
WI-NRS pruritus ^e	X ^s								
POEM ^f	X ^s	X	X		X		X		X
Local Tolerability Assessment ^g	X	X	X		X		X		X
CDI-2, PHQ-8, PHQ-A, C-SSRS ^h	X ^s	X	X		X		X		X
DLQI, CDLQI, IDQOL, DFI ⁱ	X ^s	X	X		X		X		X
Medical Photography ^j	X ^s	X	X		X		X		X
Urine pregnancy test ^k	X ^s	X	X		X		X		X
PK draws ^l									X

Study Procedure	Day 1	Wk 4	Wk 12	Wk18	Wk 24 ^t	Wk 30	Wk 36	Wk 44	Wk 52/ET
Visit #	1(Week 4) of ARQ-151-311 or ARQ-151-312 or ARQ-151-315	2	3	Phone Visit	4	Phone Visit	5	Phone Visit	6
Visit Window		+/- 3 days	+/- 7 days	+/- 7 days	+/- 7 days	+/- 7 days	+/- 7 days	+/- 7 days	+/- 7 days
Dispense study medication kit ^m	X	X	X		X		X		
Drug application and Parents/Caregivers training in clinic	X								
Dispense/review diary ⁿ	X	X	X		X		X		X
Maintenance Dosing Determination ^o		X	X		X		X		
Weigh study medication ^p	X	X	X		X		X		X
Compliance Determination ^q		X	X		X		X		X
Adverse event assessment ^r	X	X	X	X	X	X	X	X	X
Concomitant medications	X	X	X	X	X	X	X	X	X
Study Exit					X ^t				X

^a Limited physical examination: skin, lungs, and heart only

^b Hematology, Serum Chemistries, and Urine Analysis will only be done in subjects \geq 12 years of age at time of enrollment in the preceding study.

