^p The entire kit (every tube) should be weighed and recorded at every visit. See IP Handling Manual for details.

^q Compliance calculation is described in the IP Handling Manual

^r Any emergent AEs will be followed in the clinic for up to one month at the Investigator’s discretion until resolved or otherwise judged as clinically stable.

^s This data will be obtained from Week 4 of ARQ-151-311/312/315 Study and used as the Day 1 data for this long-term safety study (ARQ-151-313).

^t Under Amendment 1, this is the final visit for Cohort-Week 24 from ARQ-151-311 and ARQ-151-312.

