4.3. Subject Participation

Subject participation involves a minimum of five clinic visits at Week 4, Week 12, Week 24, Week 36 and Week 52 of treatment. There will be three phone visits conducted at Weeks 18, 30 and 44. (For Cohort-Week 24, subject participation involves a minimum of three clinic visits at Week 4, Week 12 and Week 24 of treatment. There will be one phone visit conducted at Week 18). The Day 1 visit of this study will be Week 4 of the ARQ-151-311 or ARQ-151-312 or ARQ-151-315 study. The baseline value for safety and efficacy will be the last observation prior to the first dose of ARQ-151 cream in either the ARQ-151 preceding study (ARQ-151-311 or ARQ-151-312 or ARQ-151-315), or this study. The anticipated maximum duration of subject participation is about 24 or 52 weeks. Subjects in the ARQ-151-311 or ARQ-151-312 or ARQ-151-315 study that choose to participate in the long-term extension study will transition directly into the ARQ-151-313 study at the Day 1 visit (Week 4 of Study ARQ-151-311 or ARQ-151-312 or ARQ-151-315).

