5.1.13. Phone Follow Up Visit

Phone Follow Up Visits will be conducted according to the Schedule of Visits and Assessments ([Section 1.3](#)) for all subjects to review any adverse event or concomitant medication changes.

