5.4. Final Study Visit – End of Study

The approximate final study visit will occur at Week 52, except for subjects in the Cohort-Week 24, where the final study visit will occur at Week 24. The procedures performed during this visit are as described in the Schedule of Visits and Assessments ([Section 1.3](#)). A 7-day scheduling window is allowed for this visit. Adverse events will be recorded as reported by the participant or and followed to resolution or stabilization (as necessary).

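### The SAP 6.6 subgroup for the change from 0.05% to 0.15% cream is defined by turning 6 on study, but no kit is dispensed after Week 36, so children who turn 6 later qualify without receiving 0.15%

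*SAP*

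**What the plan says.** SAP 6.6 sets out an extra subgroup so that the efficacy and safety profile of children who change concentration can be understood. It consists of ARQ-151-315 rollovers aged 5 at the start of this study "who turn 6 years old during this study and so, will be switched from roflumilast cream 0.05% to roflumilast cream 0.15"%. Its endpoints are left open, to be settled before the final lock of ARQ-151-315.

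Protocol 4.1 gives the rule: "the subject will be switched from ARQ-151 cream 0.05% to ARQ-151 cream 0.15% at his/her first scheduled post-birthday visit".

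The visits are in Protocol 4.3: "Subject participation involves a minimum of five clinic visits at Week 4, Week 12, Week 24, Week 36 and Week 52 of treatment", and "There will be three phone visits conducted at Weeks 18, 30 and 44". Protocol 5.1.13 says the phone contacts are held "to review any adverse event or concomitant medication changes". In the Protocol 1.3 schedule the row "Dispense study medication kit" is marked at Day 1 and Weeks 4, 12, 24 and 36, and not at Weeks 18, 30, 44 or 52. Protocol 5.4 adds: "The approximate final study visit will occur at Week 52". The shorter follow-up does not apply to these children: the Week 24 footnote in Protocol 1.3 reads "this is the final visit for Cohort-Week 24 from ARQ-151-311 and ARQ-151-312".

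SAP 11 separately summarises the percentage of study days on each dose for ARQ-151-315 rollovers who turn 6, and plans listings of exposure and of kit and tube accountability.

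**The concern.** The definition uses age as a stand-in for exposure. It identifies children who changed concentration only if every sixth birthday is followed by a visit that can supply 0.15%, and the schedule does not provide for that after Week 36. Nearly every 5-year-old who completes 52 weeks will turn 6, so the criterion in practice selects children aged 5 at entry and filters out almost none of those who stay on 0.05%.

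At stake is whether the subgroup answers its stated question. No other planned outcome analysis does so. SAP 5 reports all ARQ-151-315 rollovers in groups labelled 0.05% or 0.15% combined, the efficacy age subgroups in SAP 6.6 use age at parent-study consent, and SAP 13.1 specifies its adverse-event summaries by age group for ARQ-151-311/312 rollovers.

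**Working it through.** The documents give no size for this subgroup and no share switched, so there is no stated figure to reproduce.

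**Inputs from the documents.** Dispensing visits after Day 1: Weeks 4, 12, 24 and 36 (Protocol 1.3). Exit: Week 52 (Protocol 5.4). Target days: 253 for Week 36 and 365 for Week 52 (SAP 5.4). Visit windows at both: ±7 days (Protocol 1.3).

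**Assumptions not in the documents.** Sixth birthdays uniform over the 52 weeks, visits on target day, no dropout, and a switch at the first dispensing visit after the birthday.

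| Birthday (weeks) | Interval length | Switch visit | Weeks on 0.05% | Weeks on 0.15% |
|---|---|---|---|---|
| 0-4 | 4 | Week 4 | 4 | 48 |
| 4-12 | 8 | Week 12 | 12 | 40 |
| 12-24 | 12 | Week 24 | 24 | 28 |
| 24-36 | 12 | Week 36 | 36 | 16 |
| 36-52 | 16 | none | 52 | 0 |

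**Share never switched.** (52 − 36)/52 = 16/52 = 30.8%. In days: (365 − 253)/364 = 112/364 = 30.8%.

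**Person-time on 0.15%.** (4×48 + 8×40 + 12×28 + 12×16)/52 = 1040/52 = 20.0 weeks per child, or 20/52 = 38.5%. Among switchers only: 1040/36 = 28.9 weeks, or 55.6% of 52.

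**Where the remaining 32 weeks per child come from.** Never-switched children: 16×52/52 = 16.0 weeks. Pre-switch time in switchers: (4×4 + 8×12 + 12×24 + 12×36)/52 = 832/52 = 16.0 weeks. Each source accounts for half, so restricting membership is not enough without a split at the switch date.

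**By visit.** If the general conventions of SAP 5.3 and 5.4 (study day and OLE visit) are applied to this subgroup, the share with any earlier 0.15% use is 0% at Week 4, 4/52 = 8% at Week 12, 12/52 = 23% at Week 24, 24/52 = 46% at Week 36 and 36/52 = 69% at Week 52.

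**Sensitivity of the 30.8%.**
- Visit windows: lowest with Week 36 seven days late and Week 52 seven days early, (358 − 260)/(358 − 1) = 98/357 = 27.5%; highest the other way round, (372 − 246)/(372 − 1) = 126/371 = 34.0%.
- Dropout of 0% to 40% by Week 52 (simulated, exponential): 30.8% falling to 29.2%.
- Seasonal birthdays: 28-33% at 10% amplitude, 26-36% at 20%.
- If 0.15% could be supplied at the Week 44 phone visit, which the schedule does not provide for: (52 − 44)/52 = 8/52 = 15.4%.

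**The case against.** The strongest reply is that the SAP 6.6 sentence joins turning 6 with being switched, and may simply mean the switched children. That reading is available, but the text then gives no class for a child who turned 6 and was not switched. Taken literally, the entry conditions are the two ages, and the switch is stated as their consequence.

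Second, the analysis is not yet specified: endpoints are open, and 6.6 does not say whether results will run by OLE visit or from the switch. This stands. It makes the by-visit percentages conditional, and it is also why the correction is cheap now.

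Third, SAP 11 and its listings would show who stayed on 0.05%. This stands too: unswitched children should be identifiable. But a summary of days on each dose links no efficacy or safety result to concentration.

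A reader might infer three stronger claims that the documents do not support:
- That a safety effect arising only on 0.15% would appear at 69% (36/52) of its true incidence, or that effects are pulled toward zero. No comparator or estimate is defined for this subgroup, switchers have 16 to 48 weeks of exposure, and SAP 13.1 also reports exposure-adjusted rates. No single attenuation factor follows.
- That the phone visits add to the loss. For (6 + 6 + 8)/52 = 38% of birthdays the next scheduled contact is a phone visit. However, the schedule numbers only clinic visits, and footnote m places the switch on the dispensing row, so the natural reading is the next dispensing clinic visit. The 30.8% already uses that reading. The footnote also refers to an IP Handling Manual that was not available here.
- That 31% is a figure of the plan. It is an expectation under stated assumptions.

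**Conclusion.** The concern holds in this form: as written, the subgroup includes children who cannot receive 0.15% under the schedule, and it has no rule for separating them. With uniform birthdays and visits on target day they are 16/52 = 31% of the subgroup, about 28-34% with the visit windows, and only about 38% of subgroup person-time is on 0.15%. The existence of the gap does not depend on those assumptions; its size does.

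The consequence is limited. The subgroup is descriptive, SAP 5.7 plans no hypothesis tests, the study's primary endpoints are untouched, and the number of children is not given. Because SAP 6.3 excludes ARQ-151-315 rollovers from the interim analyses, no interim result is affected. It should still be corrected, since the rule followed literally serves its own purpose poorly.

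**What to change.** In SAP 6.6:

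- Define the subgroup as ARQ-151-315 rollovers who started this study on 0.05% and have a documented first application of 0.15% in this study. Requiring only one dose of 0.15% would be too loose: SAP 3.4 assigns concentration by age on Day 1, so a rollover already 6 that day would enter without ever having changed.
- Split events, visits and person-time at the date of first 0.15% application, and give exposure-adjusted rates before and after, each with its own exposure as denominator.
- Report separately the children who turned 6 but did not switch.

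The cost is SAP wording, before the ARQ-151-315 lock when the endpoints are due to be settled anyway. There are three downsides. The subgroup shrinks to about 36/52 = 69% of those who turn 6, under the same assumptions. Membership selects on reaching the switch visit, so a child who stopped between birthday and visit, for example for an adverse event or lack of efficacy, drops out of it; the separate report keeps such children in view. The before/after comparison is confounded with time on study and age, and should be presented as descriptive only.

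The sponsor must also reconcile the switch wording in Protocol 1.1, 1.3 and 4.1 and in the SAP with the phone visits and with the Week 52 visit, where no kit is dispensed. How that is resolved is a clinical decision on which this review takes no position.
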